SA1: To compare functional performance benefit between HD participants randomized to vitamin D supplementation and placebo. Function will be measured by the 50ft timed walk, the Timed Up and Go test (TUG), a timed stair climb, the Chair Raise test, the Functional Reach test, postural sway, and muscle handgrip, hip flexor and knee extensor strength.

H1: We hypothesize that a greater proportion of the subjects will demonstrate an improvement in postural sway in the treatment group than in the placebo group.

SA2: To compare cognitive function as measured by neuropsychological testing between HD participants randomized to vitamin D supplementation and placebo.

H2: We hypothesize that a greater proportion of the subjects will demonstrate an improvement in the treatment group than in the placebo group.

SA3: To compare the Self-report of physical activity and quality of life (QOL) between HD participants randomized to vitamin D supplementation and placebo.

H3: We hypothesize that the total score on the Physical Activity Scale for Persons with Physical Disabilities (PASIPD) and the QOL scores will significantly improve in the treatment groups versus no change in the control group.

SA4: To compare immune function between HD participants randomized to vitamin D supplementation and placebo.

H4: We hypothesize that immune function will be increased in the treatment group versus no change in the control group.

B) BRIEF REVIEW OF RESULTS OF OTHERS AND CURRENT STATE OF KNOWLEDGE

Pathophysiology and Management of Vitamin D and Deficiency in HD Patients:

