ng/ml, the frequency of administration will be reduced to once a month. The participants will receive supplementation for a total of 6 months. At this time, vitamin D levels will be reassessed and participants will undergo follow-up functional assessments, and cognitive and immune testing. Subjects will be recruited from the outpatient hemodialysis (HD) unit which is located on the fourth floor of the James J. Peters VAMC.

Primary Outcomes (tested at Baseline, 3 months and 6 months):

- 1) Neuromuscular functional performance using the 50ft timed walk, the TUG, a timed stair climb, and the Chair Raise test, (48)
- 2) Postural stability using a Sway meter (NeuroCom International, Inc., Clackamas, OR) that measures displacement of the body at the level of the waist in 30 second periods (49) and the Functional Reach test.
- 3) Muscle hand grip strength using the Harpenden Hand Grip dynamometer (50) and hip flexor and knee extensor strength using a Push-Pull Muscle Strength dynamometer.

Secondary Outcomes:

- 1) Cognitive function (tested at Baseline, 3 and 6 months):
 - a) Mental Status: Mini-Mental Status Exam (MMSE) (51) and Short Blessed Test (SBT) (52);
 - b) Memory: California Verbal Learning Test – II (CVLT-II) (53);
 - c) Language: Category Fluency and Controlled Oral Word Association Test (COWAT) (54);
 - d) Attention and Processing Speed: Trails A (55), Digit Span (56), Symbol Digit Modality Test (SDMT) (57), and Stroop Color and Word (58)
 - e) Executive Function: Trails B (55) and Stroop Color-Word (58).
- 2) Self-assessment of Physical Fxn and Health (tested at Baseline, 3 months and 6 months):
 - a) Physical Activity Scale for Persons with Physical Disabilities (PASIPD) (59)
 - b) NIH PROMIS (v1.0 Item Banks): Global Health Physical Function, Pain, Fatigue, Sleep, Emotional Distress (60)
 - c) Beck Depression Inventory (BDI)
- 3) Immunology (tested at Baseline, 6 months)
 - a) Serum cytokines

This study will be performed over two years.

TABLE 1. Study Flow Sheet	BL 1	BL 2	Month 1	6 weeks	Month 2	Month 3	Month 4	Month 5	Month 6
Week:	0	0 ₂	4	6	8	12	16	20	24
Physical Function Assessment 50ft walk, TUG, stair climb, Chair Raise, Functional Reach, Sway, Hand Grip, Hip & Knee Strength		X				X			X
Self - Assessment PASIPD & NIH PROMIS (short forms): Physical Fxn, Pain, Fatigue, Global Health, Sleep, Emotional Distress, BDI		X				X			X
Cognitive Impairment Tests									

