There is little information on the effect of vitamin D replacement therapy and change in cognitive function. Based on previous studies that demonstrated a correlation between poor performance and vitamin D deficiency, we expect vitamin D supplementation to improve SBT and MMSE scores (27, 30, 61). Of note, the cognitive function tests are our secondary outcome variables and we expect to gain empirical information after performing exploratory analyses regarding the effect of vitamin D replacement on cognitive function as part of this pilot study. A demonstration of improvement in neuromuscular and/or cognitive function would lead to the immediate implementation in clinical practice of 25-OH vitamin D supplementation in the care of HD patients who are vitamin D deficient and a future larger study to demonstrate dosing and length of time for maintenance of sufficient vitamin D levels to retain this positive effect.

Statistical Analysis Plan: Subjects will be randomized in a prospective, two-group, randomized study design utilizing a convenience sample of patients on hemodialysis. Subjects will be randomized to the treatment (Vit D) or placebo groups using a 2 to 1 block randomization determined from a web-based program (<http://www.randomization.com>). Subjects will be grouped in order of consenting such that the first 6 subjects will be in block 1, the next 6 in block 2, and so on. Five blocks will be performed. Each block will contain 6 subjects (2:1), with 4 subjects being randomized to vitamin D treatment to 2 subjects being randomized to the control group. Percent change scores will be calculated for both time points after treatment (3 or 6 month values – Baseline)/ Baseline * 100 for all primary outcome dependent variables (50ft timed walk, TUG, timed stair climb, Chair Raise, Functional Reach, postural sway, handgrip strength, and flexor/abduction strength) for each subject in both groups.

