The primary analysis for functional and cognitive outcomes will use the responder analysis described above. Additional secondary analyses will be performed on the primary outcome variables. In the first analysis, the percent change variables will be used for the group comparisons and analyzed by one-way analysis of variance (ANOVA) ($Y_1 = \%$ change; $X_1 = \text{Group}$). The percent change variable has the advantage of being easily analyzed in an analysis of covariance (ANCOVA) model if controlling variables are identified. For example, years on hemodialysis (HD y) may be need to be controlled for and as such this model would be $Y = \%$ change; $X_1(\text{HD y}) + X_2(\text{Group})$. The second analysis to be performed on the primary outcome variables will be the more traditional two-factor mixed model (2x3 table), where the between factor is Group (treatment, placebo) and the repeated measures (i.e. the within-subjects) factor is Time (BL, 3 and 6 months). In the case of missing data we will use 2 imputation methods. First as is commonly done in clinical trials of cognitive impairment and dementia we will use the last observation carried forward for missing terminal visits. We will compare results from these methods with a variety of other imputation methods. For missing data within a specific test, we will assign the average the remaining domains for those that do not complete a domain. Other imputations will include assigning values from 1) a regression across the available time points, and 2) assigning the average value of all subjects within in the group. We will compare results using these different imputations.

Significant main effects will further be explored by single degree of freedom post hoc analyses. For the secondary analyses covariates will be used including age and education adjusted T scores will be used for the baseline versus 6 month comparisons by performing a 2x2 repeated measures ANOVA. For

the self assessment variables (PASIPD and NIH PROMIS) percent change will be calculated as previously described and analyzed by one-way ANOVA as described for the primary outcome variables above.

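### PASIPD and PROMIS scores are analysed only as percent change from baseline, which weakens power and makes the SA3 result hard to interpret; the comparison between arms remains valid

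*Combined protocol and SAP*

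**What the plan says.** The Statistical Analysis Plan (section C) names PASIPD and NIH PROMIS together and states that for them "percent change will be calculated as previously described and analyzed by one-way ANOVA". The formula referred to is given for the primary outcomes and applied per subject: "3 or 6 month values – Baseline)/ Baseline * 100" (the opening bracket precedes the quoted words). The model has percent change as outcome and group as the only term.

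Nothing else in the plan clearly covers these instruments:
- The responder analysis is for functional and cognitive outcomes, and the Power analysis gives response thresholds only for TUG, sway and strength.
- The raw-score mixed model is limited to other variables: "The second analysis to be performed on the primary outcome variables will be the more traditional two-factor mixed model".
- The 2x2 repeated-measures ANOVA uses T scores adjusted for age and education, which reads as cognitive testing.
- The optional ANCOVA keeps percent change as the outcome. Its example covariate is years on hemodialysis, not the baseline score.

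There is no rule for a zero or very low baseline, and the PROMIS scoring metric is not stated. Under Specific Aims, H3 predicts that the PASIPD total and the QOL scores "will significantly improve in the treatment groups versus no change in the control group".

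**The concern.** Walking times and strength have a physical zero, so a ratio to baseline has a fixed meaning. A questionnaire score need not. Dividing by its baseline gives the same gain in points a different weight according to where a person starts and where the scale's zero lies. Low baselines can produce very large percentages. The average of such ratios also tends to be positive when nothing has changed, which matters because H3 describes an unchanged placebo arm.

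Two things are at stake: power in a 20 versus 10 comparison, and whether the pilot gives usable estimates. One goal under Specific Aims is to gain experience with outcome measures for a pivotal trial. Score differences and their SDs serve that purpose; unstable percentages do not.

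**Working it through.** **Inputs from the documents.** Percent-change formula and one-way ANOVA (Statistical Analysis Plan); 20 vitamin D and 10 placebo (Research Design and Methods). The plan states no power or effect size for PASIPD or PROMIS, so there is no figure of its own to reproduce. Its sample-size figures concern the responder endpoint.

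**Assumed.** Score means, SDs, CVs, shapes, the baseline to follow-up correlation r, effect sizes, two-sided 5% tests, and all 30 participants analysed.

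**1. Scale origin.** A 4-point gain is 4/40 = +10.0%, 4/50 = +8.0% or 4/60 = +6.7%. Move the zero point by 20 and the same gains become 4/20 = +20.0%, 4/30 = +13.3% and 4/40 = +10.0%.

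**2. Low baselines.** A baseline of 0 has no percent change. A move from 1 to 5 is +400%. One such participant shifts the placebo mean by 400/10 = 40 percentage points.

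**3. Rise with no true change.** Two people who swap scores of 10 and 20 give +100% and -50%: mean +25%, mean raw change 0. For lognormal scores with equal mean and CV at both visits, and r on the log scale, the expected percent change is 100 × [(1 + CV²)^(1 - r) - 1]:
- CV 0.6, r 0.7: 1.36^0.3 = 1.097, or +9.7%
- CV 1.2, r 0.5: 2.44^0.5 = 1.562, or +56.2%

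Simulation gives about +9% to +56% over this grid. If r is instead the correlation of the raw scores, the ratio is (1 + CV²)/(1 + r·CV²). The same corners are then 1.36/1.252 = 1.086 (+8.6%) and 2.44/1.72 = 1.419 (+41.9%).

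For a symmetric score with mean 42 and SD 8, CV = 8/42 = 0.19 and the rise is roughly CV²(1 - r): 0.036 × 0.5 = 1.8% at r 0.5, and 0.036 × 0.3 = 1.1% at r 0.7.

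**4. Type I error.** Simulated at 20 versus 10 with no effect, percent-change ANOVA rejects in about 4-5% of trials, because the rise in step 3 occurs in both arms.

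**5. Power, symmetric score (mean 42, SD 8, 6-point effect).**

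| r | Percent-change ANOVA | Raw ANCOVA |
|---|---|---|
| 0.5 | 40% | 56% |
| 0.7 | 60% | 73% |

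**6. Power, skewed score (lognormal, effect 0.8 SD on the log scale).** Over CV 0.6-1.2 and r 0.5-0.7, percent-change ANOVA has 25-65% and log ANCOVA 59-79%. At r 0.85 the gap shrinks to 90-94% against 96-97%. Individual settings, subject to a few points of simulation error:

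| CV, r | Percent change | Raw ANCOVA | Log ANCOVA |
|---|---|---|---|
| 0.6, 0.5 | 39% | 48% | 62% |
| 0.6, 0.7 | 65% | 63% | 80% |
| 1.2, 0.7 | 52% | 44% | 78% |
| 1.2, 0.85 | 90% | 70% | 96% |

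**7. Power, skewed score with an effect added in points (0.8 SD; r on the raw scale).** Percent change against raw ANCOVA is 63% against 73% (CV 0.5, r 0.6), 91% against 91% (CV 0.5, r 0.8), 72% against 79% (CV 1.0, r 0.6) and 93% against 94% (CV 1.0, r 0.8).

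**The case against.** The strongest reply is that SA3 compares randomised arms and no within-placebo test is planned. The arithmetic rise is common to both arms, so the planned test keeps its size. This stands. A reader might infer that the method could create a false vitamin D effect on SA3; the plan's between-group model and step 4 do not support that.

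A reader might also infer that percent change breaks down for PROMIS as it could for PASIPD. The documents give no PROMIS metric, range or mean, and on a score well away from zero the rise is only 1-2%. Low PASIPD baselines are also undocumented. Muscle weakness and fatigue in this population make them plausible, but participants must be able to walk and are asked to climb 13 stairs. The +56% is the extreme corner of an assumed grid.

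Nor is raw ANCOVA better everywhere. In step 6 it gives no gain, or does worse, at r of 0.7 and above. The advantage of the log version there is partly built in, since the data were generated on that scale. With an effect added in points (step 7) raw ANCOVA does as well or better. The ranking therefore depends on the assumed model.

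The optional ANCOVA softens the point only slightly, because it neither names the baseline score nor drops percent change as the outcome.

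**Conclusion.** The concern holds in a limited form. Dependence on the scale origin and failure at a zero baseline follow from the plan's own formula and need no outside data. The loss of power is 13 to 16 percentage points for the assumed symmetric score (73 - 60 and 56 - 40). For a skewed score against log ANCOVA it is larger at r of 0.5 to 0.7 and small at 0.85. The placebo rise could misdescribe H3's unchanged control arm only if PASIPD is skewed with low baselines; for a PROMIS-like symmetric score it is negligible.

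All sizes rest on assumed distributions and correlations. False positives are not at issue. These are secondary outcomes in a 30-person pilot, so the priority is low to moderate.

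**What to change.** In the Statistical Analysis Plan, replace percent-change ANOVA for the self-assessment variables with ANCOVA of the follow-up score on arm and baseline score:
- **Each PROMIS short form:** use the raw score, state the scoring metric, and report the adjusted difference in score points with its confidence interval.
- **PASIPD total:** pre-specify either ANCOVA on log(x + c), with c fixed before unblinding and the effect reported as a ratio, or a rank-based ANCOVA. Do not rely on raw ANCOVA here. Give raw point summaries by arm as description.
- **BDI:** it is listed with the self-assessments among the secondary outcomes, but the analysis text names no method for it. It is not assigned to percent change; it can be handled in the same way as the other questionnaires.

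The cost is SAP wording only: the baseline scores are already collected, and no visit or participant is added. The downside is that the PASIPD effect is no longer expressed directly in score points, and the log version depends on the choice of c.

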The current standard of care involves the administration of active 1,25 OH vitamin D intravenously during dialysis. The dose is determined by the patient's private nephrologist based on monthly laboratory reports. Because 25-OH vitamin D supplementation is not currently recommended in HD patients, only a limited number of studies have examined the efficacy and safety of cholecalciferol and ergocalciferol vitamin D replacement in this population. Currently two studies have evaluated the safety and efficacy of 25-OH replacement in HD patients over a 6 month duration. In one study, oral 25- OH vitamin D was given daily in doses ranging from 400 units to 1200 units based on severity of vitamin D deficiency (45). All patients had 25-OH vitamin D levels < 30 ng/mL and 87% achieved levels > 30 ng/mL without evidence of toxicity. In another study in which 52% of patients had 25-OH < 15 ng/ml and 92% had levels < 30 ng/mL; after 6 months of treatment using 50,000 U of ergocalciferol, 94% of patients had 25-OH levels > 30 ng/mL and none were < 15 ng/mL (2). The treatment was well tolerated without evidence of toxicity. The safety of cholecalciferol administration to HD patients was demonstrated after 100,000 units of cholecalciferol were given monthly for 15 months; vitamin D deficiency was corrected in nearly 90% of patients (46). Using more frequent doses of vitamin D, 20,000 units of cholecalciferol were given weekly to HD patients with levels < 15 ng/mL for 9 months and followed up with maintenance dosing at 20,000 per month for 15 months; vitamin D was well tolerated and without adverse effects, however only 57% of patients achieved levels > 30 ng/mL which is considered optimal (47). Given the safety of these studies, we propose administering 50,000 units of cholecalciferol every week with level monitored monthly to insure response to treatment and to adjust dose if levels raise > 60 ng/mL. Patients in both arms of the study will receive the current standard of

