We propose to perform a prospective, randomized, double-blind placebo controlled trial. Patients will be included if they are: 1) receiving outpatient hemodialysis at the James J. Peters VAMC, 2) receiving IV vitamin D therapy according to National Kidney Foundation guidelines, 3) between the ages of 45-89 years, 4) a veteran outpatient or stable community living center patient, and 5) able to ambulate independently or with an assistive device for at least 20 feet. Exclusion criteria include: 1) 25-OH vitamin D level \geq 25 ng/ml, 2) hypercalcemia, 3) active malignancy within 6 months, 4) receiving intravenous antibiotics for infection, 5) history of dementia, 6) hemoglobin $<$ 8.5g, 7) history of conditions that interfere with postural instability (e.g. cerebellar disease, vestibular disease or any others that may present), and 8) poor compliance with dialysis treatments (history of skipping \geq 2 treatments per month for $>$ 2 months). A 25-OH vitamin D level of $<$ 25 ng/ml level was chosen based on previous studies that have shown that patients have the greatest improvement in muscle strength when levels below this threshold are increased. Patients will first be identified based on the inclusion criteria, then informed about the study and consented. Those who meet the exclusion criteria will be randomized to treatment or placebo. Enrolled participants will be randomized 2:1 to receive vitamin D (n=20) or placebo (n=10) for 6 months. All participants will be tested twice over two weeks to establish baseline values. Following baseline testing, the treatment group will receive 50,000 IU (standard replacement therapy) of oral cholecalciferol or placebo. The initial dose of cholecalciferol will be 50,000 IU weekly for 6 weeks. Vitamin D levels will then be measured. Participants who still have Vitamin D insufficiency (\leq 35 ng/ml) will remain on 50,000 IU of cholecalciferol for another 6 weeks, at which point Vitamin D levels will be measured again. Participants who reach 25-OH levels $>$ 35 ng/ml will have their dosing regimen lessened to 10,000 IU weekly (maintenance dose) for the remainder of the 6 months. Participants receiving placebo will start taking the placebo maintenance dose after the first 6 weeks. For safety monitoring, 25(OH) vitamin D₃ levels will also be re-measured at monthly intervals and followed by an independent medical monitor. In patients who have serum vitamin D levels \geq 60

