Immune Function Analysis Primary analysis will compare study subjects who had a 25-OH level > 35 ng/ml to study subjects who remained at a level ≤ 35 ng/ml (Vitamin D deficient/insufficient). Potential confounders that will be examined include age, 25-OH Vitamin D level at Baseline, time on HD, sex, and ethnicity. Variables that differ significantly between treatment arms at an alpha of 0.01 and are significantly related to the immune outcomes at an alpha of 0.05 will be included in multivariable analysis. If potential confounders meet the criteria for inclusion, the multivariable analysis will be the primary analysis.

a. Basic Information (Even if described under “Procedures”, list the information requested below where pertinent.)

1. What procedures will be used (i.e. biopsy, surgical operation, interview, experimental diet, infusion, drug administration, etc.) and with what frequency?

All participants will have their serum Vitamin D levels tested twice over two weeks to establish baseline values. Following baseline testing, the treatment group will receive 50,000 IU (standard replacement therapy) of oral cholecalciferol or placebo. The initial dose of cholecalciferol will be 50,000 IU weekly for 6 weeks. Vitamin D levels will then be measured. Participants who still have Vitamin D insufficiency (≤ 35 ng/ml) will remain on 50,000 IU of cholecalciferol for another 6 weeks, at which point Vitamin D levels will be measured again. Participants who reach 25-OH levels > 35 ng/ml will have their dosing regimen lessened to 10,000 IU weekly (maintenance dose) for the remainder of the 6 months. Participants receiving placebo will start taking the placebo maintenance dose after the first 6 weeks. 25(OH) vitamin D₃ levels will also be re-measured at monthly intervals and followed by an independent medical monitor. In patients who have serum vitamin D levels ≥ 60 ng/ml, the frequency of administration will be reduced to once a month. The participants will receive supplementation for a total of 6 months.

The following outcomes will be tested at **Baseline, 3 months and 6 months**:

Physical Functional assessments:

- 1) Neuromuscular functional performance using the 50ft timed walk, TUG test, a timed stair climb, and Chair Raise test, (48)
- 2) Postural stability using a Sway meter (NeuroCom International, Inc., Clackamas, OR) that measures displacement of the body at the level of the waist in 30 second periods (49) and the Functional Reach Test.

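### SA4 asks whether immune function differs between the randomised arms, but the only immune analysis planned splits participants by achieved 25-OH level, so SA4 gets no randomised answer

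*Combined protocol and SAP*

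**What the plan says.** Section A (Specific Aims) sets the question by randomised arm: "SA4: To compare immune function between HD participants randomized to vitamin D supplementation and placebo". Its hypothesis H4 is that "immune function will be increased in the treatment group versus no change in the control group".

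The Immune Function Analysis paragraph of the Statistical Analysis Plan (section C) defines one contrast: "Primary analysis will compare study subjects who had a 25-OH level > 35 ng/ml to study subjects who remained at a level" at or below 35 ng/ml. Treatment arm appears in that paragraph only in the rule for choosing adjustment variables, which starts "Variables that differ significantly between treatment arms at an alpha of 0.01" and also requires a relation with the immune outcome at 0.05. If any variable qualifies, the adjusted model becomes primary, but the contrast stays the same.

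Serum cytokines are measured at baseline and 6 months (Secondary Outcomes, item 3).

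Research Design and Methods uses the same 35 ng/ml figure for titration. Participants at or below it after six weekly doses "will remain on 50,000 IU of cholecalciferol for another 6 weeks, at which point Vitamin D levels will be measured again". Those above it move to 10,000 IU weekly.

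**The concern.** Achieved 25-OH level is a result of treatment, absorption, adherence, body size and health. Grouping by it gives up the protection of randomisation. All or nearly all of the high group will be treated. The low group pools placebo participants with treated participants who did not reach the cut-off. A difference between the two can reflect who attains the level, not what vitamin D does.

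Followed exactly, the plan would report this non-randomised comparison as the primary immune result of a randomised, double-blind trial, and it could be read as a treatment effect when the pivotal trial is designed. The arm comparison named in SA4 would not be reported at all.

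**Working it through.** **1. Is a by-arm immune analysis written elsewhere?** The analyses in the Statistical Analysis Plan are:

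| Analysis | Outcomes it is assigned to | Contrast |
|---|---|---|
| Responder analysis | functional and cognitive | arm |
| Percent-change ANOVA/ANCOVA | primary (functional) variables | arm |
| 2x3 mixed model | primary (functional) variables | arm and time |
| 2x2 repeated-measures ANOVA, baseline vs 6 months | age- and education-adjusted T scores | arm and time |
| Percent-change ANOVA | PASIPD, PROMIS | arm |
| Immune Function Analysis | immune outcomes | achieved level >35 vs ≤35 |

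None of the by-arm analyses names cytokines. The plan gives no power or effect size for immune outcomes, so there is no stated figure to reproduce.

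**2. Who is in the low group?** Allocation is 20:10. The documents give no attainment rate for >35 ng/ml. The section on dosing in HD patients cites three studies with 57% ("however only 57% of patients achieved levels > 30 ng/mL"), 87% and 94% ("94% of patients had 25-OH levels > 30 ng/mL and none were < 15 ng/mL") above 30 ng/ml. I use these as a rough proxy and assume that no placebo participant exceeds 35.

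- 57%: 20 × 0.43 = 8.6 treated in the low group; 8.6/18.6 = 46% of it.
- 87%: 20 × 0.13 = 2.6; 2.6/12.6 = 21%.
- 94%: 20 × 0.06 = 1.2; 1.2/11.2 = 11%.

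**3. Exposure within the groups.** Scheduled dose by week 12:

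- still ≤35 at week 6: 12 × 50,000 = 600,000 IU
- >35 at week 6: 6 × 50,000 + 6 × 10,000 = 360,000 IU

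The low group can therefore mix zero exposure with the highest scheduled exposure.

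**4. Type I error with no treatment effect.** Simulation: 40,000 replicates per cell, 20 vs 10, normal outcome with SD 1, pooled t-test at two-sided 0.05. The correlation between achieved level and outcome in the treated arm is an assumption.

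| Attainment | corr. 0 | corr. 0.3 | corr. 0.5 |
|---|---|---|---|
| 57% | 5% | 14% | 29% |
| 87% | 5% | 7% | 12% |
| 94% | 5% | 6% | 7% |

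By randomised arm it is 5% in every cell.

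**5. Does the confounder rule repair this?** Read literally, a continuous covariate must differ between arms by t(0.995, 28 df) × √(1/20 + 1/10) = 2.763 × 0.387 = 1.07 SD to pass at 0.01. Randomisation makes that rare. I simulated one baseline covariate that carries the whole correlation (0.3 or 0.5). It differs between the level groups by 0.17 to 0.78 SD, yet is admitted in about 1% of trials. Type I error is 5.6% to 29.4% with the rule and 5.7% to 29.6% without it. Always adjusting for that covariate gives 5%.

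**6. Estimates and power for a true 1.0 SD effect** (zero level-outcome correlation, all 30 analysed):

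| Attainment | All treated benefit: split | All treated benefit: by arm | Only attainers benefit: split | Only attainers benefit: by arm |
|---|---|---|---|---|
| 57% | 0.55 SD, 24% | 1.0 SD, 70% | 1.00 SD, 72% | 0.57 SD, 25% |
| 87% | 0.81 SD, 53% | 1.0 SD, 70% | 1.00 SD, 74% | 0.87 SD, 56% |
| 94% | 0.90 SD, 61% | 1.0 SD, 70% | 1.00 SD, 72% | 0.94 SD, 64% |

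The split can therefore understate or overstate the randomised effect, depending on who benefits.

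**The case against.** The mismatch of contrasts is hard to dispute. The counter-arguments concern its size and weight.

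- **Attainment may be high.** The 57% comes from a regimen of 20,000 units weekly and then monthly, against 50,000 IU weekly here. The 87% and 94% come from different agents, and all three use 30 ng/ml as the cut-off. The plan's wording can also be read as ever versus never above 35, and with repeated draws few treated participants might stay low. This stands: at 94% attainment the inflation is only to 6% or 7%. But no classifying visit is named, so the reading is not fixed. On an ever-versus-never reading, only persistent non-attainers would bring the dose mix of step 3 into the low group.
- **Treatment arms may mean the level groups.** If the screen is applied to level groups, it helps in part. At 57% attainment, type I error falls from 30% to 13.5% (correlation 0.5) and from 12.8% to 8.7% (0.3). At 87% and 0.5 it falls from 12.2% to 8.8%. Inflation remains, and the wording would need correcting.
- **Dropout.** The plan allows for 33%. At 13 vs 7, by-arm power for 1.0 SD is 52%, not 70%, and the worst type I error is 19%, not 29%. This changes the figures but not the conclusion.
- **Weight.** Immunology is a secondary outcome of a 30-person pilot, and the data would allow a by-arm comparison at any time. That is true of the data. SA4 is nevertheless a numbered aim with a directional hypothesis, and the plan labels the level split primary.

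**Conclusion.** The concern holds and should be fixed. The plan contains no randomised answer to SA4; this follows from the text and needs no assumption.

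The size of the distortion is uncertain. It runs from none, if achieved level is unrelated to immune outcome, to a type I error of 29% at 57% attainment and a correlation of 0.5. Those figures rest on proxy attainment rates, an assumed correlation, no placebo participant above 35 ng/ml, and 30 completers. The direction of any error in the effect estimate cannot be stated in advance. The functional primary analysis is not affected.

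**What to change.** Rewrite the Immune Function Analysis paragraph:

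- **Primary:** compare the 6-month cytokine value by randomised arm, preferably adjusted for its baseline value, with no significance-based confounder screen. Decide on a log scale in advance, from the expected skewness. Name the cytokines and the direction that counts as increased immune function.
- **Exploratory:** keep >35 vs ≤35 ng/ml, labelled as non-randomised. State the visit, or the ever/never rule, that classifies a participant. Prespecify the covariates, for example from the five already listed, instead of selecting them by differences between arms. With about 30 participants a short list is better, and sex may not vary: the unit's earlier sample of 40 was all male.

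This costs SAP wording only, since arm and both cytokine measurements are already collected. The statistical price is power if benefit requires attainment: 25% by arm against 72% for the split at 57% attainment and a 1.0 SD effect in attainers. Even then the arm difference is the effect that SA4 asks for.
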